# 13 DATA MANAGEMENT

The standard procedures for handling and processing records will be followed as per GCP and the data management standard operating procedures of the contract research organization (CRO). A comprehensive Data Management Plan will be developed and approved by a representative of the Data Management CRO and the Sponsor.

### 13.1 Database Lock

The database will be locked in order to protect write access after the following preconditions are fulfilled:

- All data are entered in the database
- All data queries have been resolved to the satisfaction of the Lead Biostatistician
- All decisions have been made regarding all protocol violators and ITT population exclusions
- The eCRF will be signed off/approved by the Site Investigator
- Written authorizations to lock the database are obtained from Renibus Clinical Data Management and the Chief Scientific Officer.

# 14 ETHICAL CONSIDERATIONS

# 14.1 Ethical Conduct of the Study

The study will be conducted in accordance with United States Title 21 CFR and the ICH E6 (R1) Guidelines of Good Clinical Practice. The Declaration of Helsinki and its most recent updates (Seoul, 2008) will be observed.

The investigator will provide the Sponsor/designee with documentation of IRB approval of the protocol and the sample informed consent document before the study may begin at the investigative site. The IRB will review the protocol as required.

The investigator will supply the following to the IRB:

Protocol Number: REN-003 (Original)

Date: 25 March 2019

- The current Investigator's Brochure and updates
- Study protocol and amendments
- Informed consent and assent document and updates
- Relevant curricula vitae
- Safety alerts
- Serious adverse reaction reports

The investigator must provide the following documentation to the Sponsor or designee:

- The IRB original approval of the protocol and the informed consent, and re-approval of the study (annual or semi-annual, per IRB guidelines)
- The IRB approvals of any revisions to the informed consent document or amendments to the protocol
- All other documents that are required by local regulatory authorities

# 14.2 Regulatory Considerations

After reading the protocol, each investigator/sub-investigator will sign a protocol signature page and return a copy of the signed page to the Sponsor/designee, while maintaining the original at the site.

# 14.3 Protocol Amendments and Study Termination

The IRB must be informed and give approval for any amendments likely to affect the safety of the subjects or the conduct of the study.

The IRB must be advised in writing of the study's completion or early termination and a copy of the notification must be provided to the Sponsor.

# 14.4 Safety Monitoring

The Sponsor's Medical Monitor and will monitor safety data throughout the course of the study. Renibus Drug Safety, or their designee, will expedite to the regulatory authorities only the suspected adverse reactions that are product-related and unexpected in accordance with FDA 21 CFR 312, FDA draft guidance (Sept 2010) on Safety Reporting Requirements for INDs, and the ICH E2A guideline.

# 14.5 Quality Control and Quality Assurance

By signing this protocol, the Sponsor agrees to be responsible for implementing and maintaining quality control and quality assurance systems with written standard operating procedures to ensure that the study is conducted and data are generated, documented, and reported in compliance with the protocol, accepted standards of GCPs, and all applicable federal, state, and local laws, rules and regulations relating to the conduct of the clinical study.

By signing this protocol, the investigator agrees to conduct the study in an efficient and diligent manner and in conformance with this protocol, generally accepted standards of GCP, and all applicable federal, state, and local laws, rules and regulations relating to the conduct of the clinical study.

Protocol Number: REN-003 (Original)

Date: 25 March 2019

The investigator also agrees to allow monitoring, audits, IRB review and regulatory agency inspection of study-related documents and procedures and provide for direct access to all study-related source data and documents. Investigators will be given notice before a quality assurance audit occurs.

The investigator shall prepare and maintain complete and accurate study documentation in compliance with GCP standards and applicable federal, state, and local laws, rules and regulations, and promptly submit to the Sponsor all forms and reports required by this protocol following completion or termination of the clinical study or as otherwise required due to any agreement with the Sponsor.

# 15 GENERAL CONSIDERATIONS

# 15.1 Discontinuation of the Study

The Sponsor reserves the right to discontinue this study or investigator's participation in this study for safety or administrative reasons at any time.

# Appendix 1 Safety Clinical Chemistry, Hematology, and Urinalysis Tests Performed by the Laboratory at Screening, During the Study, and at Follow-up (EOS)

# Clinical Chemistry

Total protein Albumin

Bicarbonate

Blood urea nitrogen (BUN)

Creatinine
Total bilirubin

Alkaline phosphatase

Glucose Sodium Potassium

Inorganic phosphate Calcium (total and ionized)

Magnesium

Gamma-glutamyl transferase Alanine aminotransferase (ALT) Aspartate aminotransferase (AST)

Cystatin-C Tin

Tin Protoporphyrin

IL-6

Total porphyrins

# Hematology

Hemoglobin Hematocrit

Erythrocyte count (red blood cells)

Differential leukocytes

Total leukocytes (white blood cells)

**Platelets** 

### Urinalysis

рН

Specific gravity

Glucose Ketones Bilirubin Urobilinogen Blood P21 HO-1

Hemopexin Ferritin

Urine sediment

Urine samples to test for SnPP response

SnPP Urinary excretion

N acetyl-beta-D-glucosaminidase (NAG) Kidney Injury Molecule-1 (KIM-1)

Neutrophil Gelatinase-Associated Lipocalin

(NGAL)
Cystatin-C
Albuminuria
Urine pregnancy test

# **Response Biomarkers**

Haptoglobin

Ferritin

Hemopexin

IL-10

P21

HO-1

Bilirubin

- Collect into serum separator tubes.
- Collect into K2 EDTA tubes.
-  Approximately 10 mL of urine required for urinalysis including sediment.
- 3' Urinary excretion to be tested in a 24-hour volume sample
- Urine dipstick: all women of childbearing potential prior to the first dose of SnPP on Study Day 1 and End of Study. Perform in the clinic using the pregnancy kit supplied by the laboratory.
-  Biomarkers run with standard Chemistry samples

7.8.3	Pharmacokinetic Concentrations and Variables	18
7.9	Interim Analysis	18

8	SAMPLE SIZE CALCULATIONS	18
9	REFERENCES	19
10	TIME AND EVENTS SCHEDULE OF STUDY PROCEDURES	20
10.1	Event Schedule – All subjects	20
11	CONVENTIONS FOR THE PRESENTATIONS OF TABLES, FIGURES AND LISTINGS	21
12	LIST OF TABLES	21

List of ACRONYMS/Abbreviations

Abbreviation	Definition
AE	Adverse event
AKI	acute kidney injury
ALT	alanine aminotransferase
ARB	angiotensin-receptor blockers
AST	aspartate aminotransferase
AUC_(0-t)	area under the concentration-time curve from time 0 to t
AUC_(0-inf)	area under the concentration-time curve from time 0 to infinity
BUN	blood urea nitrogen
CFR	Code of Federal Regulations
CIOMS	Council for International Organizations of Medical Sciences
CKD	chronic kidney disease
CL	clearance
Cr	creatinine
CRO	contract research organization
ECG	electrocardiogram
eCRF	electronic case report form
EDC	electronic data capture
FDA	Food and Drug Administration
FeS	Iron sucrose
GCP	Good Clinical Practice
GFR	glomerular filtration rate
GLP	Good Laboratory Practice
HO-1	Heme oxygenase
Hp	Haptoglobin
ICF	informed consent form
ICH	International Conference on Harmonisation
ICSR	Individual Case Safety Report
IEC	Independent Ethics Committee
IL-6	Interleukin 6
IL-10	Interleukin 10
IND	investigational new drug
IRB	Institutional Review Board
ITT	Intent-to-Treat
KIM-1	Kidney Injury Molecule-1
λz	elimination rate constant
MedDRA	Medical Dictionary for Regulatory Activities
MITT	Modified Intent-to-Treat
NAG	N acetyl-beta-D-glucosaminidase
NGAL	Neutrophil Gelatinase-Associated Lipocalin
NOAEL	no-observed-adverse-effect level
POC	Proof of Concept
PK	Pharmacokinetic(s)
PP	Per Protocol
SAS	Statistical Analysis System
SnPP	Stannous Protoporphyrin
TEAE	treatment emergent adverse event
T_½	elimination half-life

Abbreviation	Definition
TFL	Tables, Figures, and Listings
T_{max}	time to maximum serum concentration
V_d	volume of distribution

1 INTRODUCTION

This is a Phase 1b single-center, dose-escalating study to evaluate the safety, tolerability, PK and pharmacodynamic effect of SnPP in healthy volunteers and in subjects with stage 3-4 CKD. The following biomarkers will be used as surrogate measures of cytoprotective activity: Haptoglobin, Ferritin, Bilirubin, Hemopexin, IL-10, and Heme Oxygenase-1. Additionally, the P21 biomarker will be monitored at various points of the study as well as urine biomarker response to SnPP.

The purpose of this statistical analysis plan (SAP) is to specifying the statistical approaches for the data analysis prior to database lock. This SAP covers the planned analyses of all data collected on the electronic case report forms (eCRFs). This SAP supersedes the statistical methods described in the clinical protocol. Deviations/changes from the planned analyses described in this SAP will be identified, with justification, in the appropriate section of the clinical study report. This SAP is developed based on the clinical study protocol REN-003, dated 29 March 2019.

The reader of this SAP is encouraged to also read the clinical protocol and other related documents for details on the planned conduct of this study. Operational aspects related to the collection and timing of planned clinical assessments are not repeated in this SAP unless relevant to the planned analyses.

2 STUDY OBJECTIVES

The primary objectives of the study are to evaluate:

1. The safety and tolerability of SnPP in healthy volunteers and in subjects with stage 3-4 chronic kidney disease (CKD).
2. The effect of SnPP on biomarkers which are potential surrogates for cytoprotective activity in healthy volunteers and in subjects with stage 3-4 (CKD).
3. To establish the optimal dose that could potentially be used in combination with iron sucrose for testing in subjects at risk for developing acute kidney injury (AKI).
4. To study the Pharmacokinetics of SnPP.

3 STUDY OVERVIEW

This is a Phase 1b, single-center, dose-escalating study to evaluate the safety, tolerability, PK and pharmacodynamic effect of SnPP in healthy volunteers and in subjects with stage 3-4 CKD. The following biomarkers will be used as surrogate measures of cytoprotective activity: Haptoglobin, Ferritin, Bilirubin, Hemopexin, IL-10, and Heme Oxygenase-1. Additionally, the P21 biomarker will be monitored at various points of the study as well as urine biomarker response to SnPP.

Subjects who meet all inclusion criteria and none of the exclusion criteria are eligible to be enrolled into the study.

The study is designed as follows:

- A screening period with baseline evaluations for study eligibility.
- If subjects meet eligibility criteria, they will receive SnPP by slow intravenous injection over a 120-minutes on study day 1.
- Subjects will stay in the clinic for the initial 24 hours after administration of SnPP and will be discharged at the end of study day 2 if no safety issues appear.
- The study will initially be dose-escalating in 3 groups of 6 healthy volunteers each, for a total of 18 healthy volunteers, evaluating escalating single dose of SnPP starting with a dose of 9 mg SnPP, followed by 27 mg SnPP, and 90 mg SnPP. Dose-escalation from one dose level to the next will only be allowed after a careful review of the safety, tolerability and PK data from the prior dose group as determined by the Data and Safety Monitoring Board (DSMB).
- After a careful review of the safety, tolerability and PK data from all dose groups from the healthy volunteer cohorts, the Data and Safety Monitoring Board (DSMB) will determine whether to proceed to the CKD cohorts. If the determination by the DSMB allows to proceed to the CKD cohorts, subjects with stage 3 CKD will be in 2 groups of 6 each, for a total of 12 subjects, evaluating escalating single dose of SnPP starting with a dose of 27 mg SnPP followed by 90 mg SnPP. Dose-escalation from one dose level to the next will only be allowed after a careful review of the safety, tolerability and PK data from the prior dose group as determined by the Data and Safety Monitoring Board (DSMB).
- After a careful review of the safety, tolerability and PK data from all dose groups from the stage 3 CKD cohorts, the Data and Safety Monitoring Board (DSMB) will determine whether to proceed to the stage 4 CKD cohorts. If the determination by the DSMB allows to proceed to the stage 4 CKD cohorts, subjects with stage 4 CKD will be in 2 groups of 6 each, for a total of 12 subjects, evaluating escalating single dose of SnPP starting with a dose of 27 mg SnPP followed by 90 mg SnPP. Dose-escalation from one dose level to the next will only be allowed after a careful review of the safety, tolerability and PK data from the prior dose group as determined by the Data and Safety Monitoring Board (DSMB).
- Subjects will be followed for 28 days after the dose of SnPP. Response biomarkers will be assessed at baseline and 2, 4, 8, 12, 18, 24, 48, 72, 96 and 168 hours after study drug administration. Safety will be assessed for up to 28 days after study drug administration.
- Blood samples for SnPP pharmacokinetic analysis will be assessed at baseline and 1, 2, 3, 4, 6, 8, 12, 18, and 24 hours after study drug administration. These data will be used in the dose escalation decision making review process along with the safety and tolerability of the previous dose. Urine samples will be collected and centrifuged and analyzed for subject responsiveness to SnPP therapy.
- Urinary Clearance of SnPP will be assessed by the measurement of tin in a 24-hour urine sample.

- Total study duration will be 29 days for each subject, in addition to a screening period of up to 14 days. Up to a total of 42 subjects consisting of 18 healthy volunteers and 24 chronic kidney disease (stage 3-4) subjects will receive single escalating doses of SnPP.

For a complete list of assessments performed throughout the study, see Time and Events Schedule ([Section 10](#)).

4 EFFICACY, PHARMOCOKINETIC, AND SAFETY VARIABLES

Efficacy Variables

- Percent change from baseline in biomarkers at each postbaseline time point
- Change from baseline in biomarkers at each postbaseline time point

The biomarkers include the following pharmacodynamic variables

- Haptoglobin (Hp)
- Ferritin
- Bilirubin
- Hemopexin
- IL-10
- Heme Oxygenase 1 (HO-1)
- P21

The urine biomarkers include the following pharmacodynamic variables

- Hemopexin
- Ferritin
- P21
- Heme-Oxygenase 1 (HO-1)

Pharmacokinetic (PK) Variables

- Maximum serum concentration (C_{max})
- Time to maximum serum concentration (T_{max})
- Area under the concentration-time curve from 0 to last time point (AUC_{0-t})
- Area under the concentration-time curve from 0 to infinity (AUC_{0-inf})
- Terminal elimination rate constant (λ_z)
- Terminal elimination half life (T_{1/2})
- Clearance (CL)
- Volume of distribution (V_z)

- Renal excretion and renal clearance (CL) of tin

Safety Variables

- Treatment-emergent adverse events
- Infusion-related reactions
- Clinical laboratory tests
- ECG
- Vital signs
- Physical exams
- Concomitant medications

5 DEFINITIONS

Terminology	Definitions
Enrolled	Subjects who signed the informed consent, meet all inclusion criterian and none of the exclusion criteria are entered into the study
Completer	Subjects who complete the End of Study (EOS) visit
Study Day	Day 1 is defined as the date subject took the study medication. Study Day for event post Day 1 is calculated as Event Date – Day 1 Date +1. Study Day for event prior to Day 1 is calculated as Event Date – Day 1 Date. Note: There is no Day 0.
Baseline	Baseline is defined as the non-missing value collected most recent to and before the study of the study medication infusion
Prior Medication	Medication started and ended prior to the study drug infusion
Concomitant Medication	Medication taken on/after the study drug infusion. Concomitant medication may start prior to study drug infusion
Treatment-emergent Adverse Event	Adverse event with onset date/time on or after the start of study drug infusion.

6 ANALYSIS POPULATIONS

The **Safety Analysis Population** will include all subjects who received study medication. This population will be used for all demographics, baseline characteristics, and safety summaries.

The **Modified Intent-to-Treat (MITT) Population** will include all subjects who received study medication and have a post-baseline efficacy assessment. This population will be used for all efficacy analysis.

The **PK Analysis Population** will include all subjects who receive study medication and provided sufficient and valid serum SnPP concentration data to allow the determination of PK parameters. This population will be used for the PK parameter summaries.

7 STATISTICAL METHODS OF ANALYSIS

7.1 General Principles

The statistical analyses will be reported using summary tables, listings, and figures (TLFs). All analyses and tabulations will be performed using SAS® Version 9.4 or later. Continuous variables will be summarized using descriptive statistics (sample size [n], mean, standard deviation [SD], minimum, median, and maximum). Categorical variables will be tabulated with number and percentage of subjects. Unless otherwise noted, percentages will be based on the number of subjects from the population, as appropriate.

Individual subject data will be provided in listings. All listings will be sorted by dose group (1 = 9mg SnPP, 2 = 27mg SnPP, 3 = 90mg SnPP), stratum (CKD Stage 3 patients and CKD Stage 4 patients versus healthy volunteer subjects), and collection date and time, where applicable,

Unless otherwise noted, tabulations of categorical data will present only those categories appearing in the data.

7.1.1 *Handling Missing Values*

7.1.1.1 Study Drug Administration Date or Time

It is expected that all necessary information on study drug administration (start and stop date and time) will be complete. Any such information that is missing and cannot be obtained through query resolution may be imputed, on a case-by-case basis, in a conservative manner that minimizes bias.

7.1.1.2 Adverse Event or Concomitant Medications Dates or Times

For AEs or concomitant medications with missing or partially missing start/stop date/time, the following imputation rules will be applied:

For partial start date/time:

- If the year is unknown, then the date will be assigned as the date and time of first dose of study treatment.
- If the month is unknown, then:
 - i) If the year matches the year of study drug administration, then the month and day will be imputed to be the first month and day on study.
 - ii) Otherwise, 'January' will be assigned.

- If the day is unknown, then:
 - i) If the month and year match the month and year of the dose of the study drug administration date, then the day of the dose of earliest study drug administration date with matching month and year will be imputed.
 - ii) Otherwise, '01' will be assigned.
- If the time is unknown, then:
 - i) If the date (day, month, and year) matches the date of an administration of study drug, then the time of dose of study drug time from that date will be imputed.
 - ii) Otherwise, '00:00' will be assigned.

For partial stop date/time:

- If the year is unknown, then the date will be assigned as the date subject discontinued from study, and the time will be set to the last time of the day ('23:59').
- If the month is unknown, then the month subject discontinued from study will be assigned.
- If the day is unknown, then the last day of the month will be assigned.
- If the time is unknown, then the last time of the day will be assigned ('23:59').

7.1.1.3 Adverse Event Severity or Relationship to Study Drug

If severity of an AE is not reported, then for tables of AEs by severity, the event will be classified as 'Severe' and clearly footnoted. If relationship to study drug is not reported for an AE, then for tables of study-drug related AEs, the event will be assigned the relationship of 'definite'. Tables presenting related AEs will include all AEs with relationships of 'possible', 'probable' or 'definite' as assessed by the investigator or defined as 'definite' when no investigator assessment is made.

7.1.2 *Multiplicity Adjustments*

Not applicable.

7.1.3 *By-Center Analyses*

This is a single-center study.

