#### **Endpoints:**

Pharmacodynamic/Safety Assessment:

Protocol Number: REN-003 (Original)

Date: 25 March 2019

The safety and tolerability of SnPP will be assessed by determining the incidence, relationship to study drug, and severity of treatment-emergent adverse events (TEAEs), withdrawals due to adverse events (AEs), and changes in vital signs, laboratory tests, changes in concomitant medication use due to AEs, and other standard safety parameters. In addition, Blood Urea Nitrogen (BUN), creatinine, Cystatin-C, Kidney Injury Molecule-1 (KIM-1), Neutrophil Gelatinase-Associated Lipocalin (NGAL), albuminuria, N acetyl-beta-D-glucosaminidase (NAG), liver enzymes, and troponin I.

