**Medical Monitor** 

Renibus Therapeutics, Inc [name]

> [contact] [contact]

E-mail: [contact]

Because the investigator is knowledgeable about the human subject (e.g., medical history, concomitant medications), administers the investigational drug, monitors the subject's response to the drug, is aware of the subject's clinical state and thus may be sensitive to distinctions between events due to an underlying disease process versus events that may be drug-related, and may have observed the event, the investigator must include an assessment of causality (i.e., whether there is a reasonable possibility that the drug caused the event) in the report to Renibus Therapeutics, Inc Copies of each report to Renibus Therapeutics, Inc. will be kept in the investigator's study file.

The investigator is responsible for complying with their IRB's requirements for reporting serious adverse events. Any expedited safety report (i.e., serious unexpected suspected adverse reaction) received from Renibus Therapeutics, Inc. should be submitted to the IRB. Copies of each report and documentation of IRB notification will be kept in the investigator's study file.

The investigator must record non-serious adverse events in the eCRF and report them to Sponsor according to the timetable for reporting (e.g., end of study). The investigator's assessment of causality is not required for non-serious adverse events.

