# 11.4 Analysis of Pharmacodynamic/Safety Endpoints

The evaluation of safety will include adverse events, clinical laboratory parameters, vital signs, physical examinations, and ECGs.

The principle of treatment emergence will be employed for the analysis of adverse event data. A Treatment emergent adverse event (TEAE) is defined to be any event that occurs during the observation period of the study and was not present at baseline, or exacerbation of a condition present at baseline.

TEAEs will be classified by the Medical Dictionary for Regulatory Activities (MedDRA). The type, incidence, timing (onset, duration), relationship, and severity of adverse events will be reported for treatment-emergent and serious adverse events. Reasons for withdrawal due to adverse events will also be reported.

Descriptive statistics, including mean, mean change from baseline, standard deviation, minimum, maximum, and median, will be presented for laboratory parameters, vital signs, and ECG parameters. The numbers and percentages of subjects with treatment-emergent laboratory, vital sign, and ECG values that meet Sponsor-defined potentially clinically significant criteria will be summarized. Categorical (low, normal, and high relative to the normal range) shifts from baseline will be summarized with the number and percentage of subjects for laboratory parameters.

All safety data will be displayed in listings.

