7.7 Safety Analyses

No inferential statistics are planned for any safety assessment.

7.7.1 *Adverse Events*

Safety assessments will be based mainly on the nature, frequency, relationship, and severity of adverse events (AEs). AEs will be coded by primary system organ class (SOC) and preferred term (PT) according to the Medical Dictionary for Regulatory Activities (MedDRA) version 22.0. The treatment-emergent adverse events (TEAEs) will be summarized by the number and percentage (n and %) of subjects in each SOC and PT. For summaries by relationship to study drug, “possibly related” will be combined with “related”, and “unlikely/remote related” will be combined with “not related.” When multiple AEs are reported with the same preferred term, the AE of the strongest relation will be included in the summary by relationship, and the AE of the most severe grade will be included in the summary by severity table.

The following AE incidence tables will be presented.

- Overview of TEAEs to include

- Number (%) of subjects who reported at least one TEAE
- Number (%) of subjects who reported at least one treatment-related TEAE
- Number (%) of subjects who reported at least one severe TEAE
- Number (%) of subjects who reported at least one serious TEAE
- Number (%) of subjects who reported at least one TEAE leading to treatment discontinuation
- TEAEs by PT sorted by decreasing order of subject incidence in the combined dose groups
- TEAEs by SOC and PT sorted alphabetically
- Study Drug-Related TEAEs by SOC and PT
- TEAEs with Grade 2+ Severity by SOC and PT

All AEs will be listed with onset/stop day, relationship to study drug, severity, action taken, and outcome. Pertinent subject information including dose group and demographics will also be included. Separate listings will be provided for TEAEs leading to study discontinuation, treatment-emergent serious AEs (TESAEs), and infusion-related TEAEs.

7.7.2 *Laboratory Test*

Hematology, biochemistry, and urinalysis test results will be summarized by dose group and visit using descriptive statistics. For quantitative laboratory parameters, both actual values and change from baseline values will be summarized.

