Treatment-emergent Adverse Event	Adverse event with onset date/time on or after the start of study drug infusion.

2. Update the Table 14.3-2.1.1.1, Table 14.3-2.1.1.2, Table 14.3-2.1.1.3, Table 14.3-2.2.1.1, Table 14.3-2.2.1.2, Table 14.3-2.2.1.3, Table 14.3-2.3.1.1, Table 14.3-2.3.1.2, Table 14.3-2.3.1.3, Table 14.3-3.1, Table 14.3-3.2 and Table 14.3-3.3 based on updated definition of 'Baseline'

All other contents remain the same

4. Signature

The following signature confirms that the activity mentioned above are completed by the responsible parties.

[name] [name] President and COO Renibus Therapeutics, Inc	10/02/2020 Date
[name] [name] Data Science Lead and Project Manager CliniOps, Inc.	October 1, 2020 Date
	Date

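### The protocol lets sites leave causality blank for non-serious AEs, and the SAP then counts every blank as drug-related with no footnote required

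*SAP*

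**What the plan says.** **Collection.** Protocol section 10.1 requires a causality assessment in serious adverse event reports, then states that the investigator's "assessment of causality is not required for non-serious adverse events".

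**Promised reporting.** The synopsis (Endpoints) says safety and tolerability will be assessed by "determining the incidence, relationship to study drug, and severity of treatment-emergent adverse events", with no restriction to serious events. Protocol section 11.4 says that "relationship, and severity of adverse events will be reported for treatment-emergent and serious adverse events".

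**Handling of blanks.** SAP section 7.1.1.3: "If relationship to study drug is not reported for an AE, then for tables of study-drug related AEs, the event will be assigned" the relationship definite. The related-AE tables take in events rated possible, probable or definite, plus those set to definite "when no investigator assessment is made". The same paragraph sets missing severity to severe and requires a clear footnote for it. It asks for no footnote on imputed causality.

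**Displays that use the rule.** SAP section 7.7.1 plans an overview row, "Number (%) of subjects who reported at least one treatment-related TEAE", and a table, "Study Drug-Related TEAEs by SOC and PT".

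**Amendment.** SAP Amendment 1 redefines baseline and updates the tables that depend on it. Otherwise, "All other contents remain the same".

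**The concern.** The protocol commits to an endpoint component that it does not require the site to record, and the SAP fills the resulting gap with the most extreme answer. Setting a missing relationship to related is a sound convention when the field is mandatory and the occasional value is lost. Here a site can follow section 10.1 to the letter, leave causality blank for every non-serious AE, and have all those events tabulated as definitely drug-related.

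Safety and tolerability is the first primary objective. Dosing is open-label with no control arm, so there is no background rate to set against the observed events, and the investigator's judgement carries much of the attribution. SAP section 7.7 plans no inferential statistics for safety, so these descriptive tables are the result. Within the two displays, an imputed event would look the same as one the investigator judged related.

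**Working it through.** The documents give no figure on this point, so there is nothing to reproduce. The check has two parts: following the text through, and an illustration of scale on stated assumptions.

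**1. Following the rules as written**

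| Step | Source | Result for a non-serious AE |
|---|---|---|
| Is causality required? | Protocol 10.1 | No |
| Is relationship to be reported? | Synopsis Endpoints; Protocol 11.4 | Yes, for TEAEs |
| What happens to a blank? | SAP 7.1.1.3 | Set to definite in the related-AE tables |
| Is the imputation flagged? | SAP 7.1.1.3 | Footnote required for severity only |
| Where does it appear? | SAP 7.7.1 | Related-TEAE overview row; related TEAEs by SOC and PT |

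SAP 7.7.1 also keeps the strongest relationship when a subject has several AEs with the same preferred term. If the imputed value is carried into that summary, it would override a weaker rating the investigator did give.

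**2. Weight of one subject**

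Cohorts have 6 subjects (SAP section 3). The 27 mg and 90 mg doses each have 6 healthy volunteers, 6 stage 3 and 6 stage 4 subjects, which makes 18. The study total is 42. One subject whose only AE is non-serious and unrated adds 1/6 = 16.7 percentage points to the related-TEAE incidence of a cohort, 1/18 = 5.6 points to a 27 mg or 90 mg group, and 1/42 = 2.4 points overall.

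**3. Inflation of the related share**

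Two quantities are assumed because the documents give neither: r, the share of TEAEs that would be judged related, and m, the share left blank (taken as independent of true relatedness).

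- Event level: tabulated share s = r(1 − m) + m. With r = 0.30: 0.30 × 0.9 + 0.1 = 37% at m = 0.1; 0.30 × 0.5 + 0.5 = 65% at m = 0.5; 100% at m = 1.
- Subject level, two independent TEAEs per subject (assumed): full-assessment share = 1 − (1 − r)²; tabulated share = 1 − (1 − s)². For example, r = 0.20 and m = 0.1 give s = 0.28, so 1 − 0.72² = 48.2% against 1 − 0.80² = 36.0%.

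| r | All assessed | m = 0.1 | m = 0.5 | m = 1 |
|---|---|---|---|---|
| 0.20 | 36.0% | 48.2% (1.34-fold) | 84.0% (2.33) | 100% (2.78) |
| 0.35 | 57.8% | 65.8% (1.14) | 89.4% (1.55) | 100% (1.73) |
| 0.50 | 75.0% | 79.8% (1.06) | 93.8% (1.25) | 100% (1.33) |

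If all six subjects in a cohort had two TEAEs and r = 0.20, the expected count in the overview row would be 6 × 0.36 = 2.2 with full assessment, against 2.9, 5.0 and 6.0 at the three values of m. At m = 0 there is no effect.

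**4. A cohort with no truly related event**

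Let p be the share of subjects with at least one non-serious TEAE and b the chance that causality is blank for such a subject (both assumed). The probability that a cohort of six shows at least one related subject is 1 − (1 − pb)⁶:

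- p = 0.3, b = 0.1: 1 − 0.97⁶ = 16.7%
- p = 0.5, b = 0.5: 1 − 0.75⁶ = 82.2%
- p = 0.7, b = 1: 1 − 0.30⁶ = 99.9%

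**The case against.** The strongest reply is that not required does not mean not collected. SAP 7.7.1 lists every AE with its relationship to study drug, which suggests that the eCRF has the field. The SAP rule is also worded as a missing-data rule, which presupposes a field that is usually filled. If sites complete it, the rule is ordinary conservative handling of stray gaps. This stands as a limit on size: the blank rate is unknown, and the m = 1 column is an upper bound that could arise only if no serious TEAE occurred, since serious events must be assessed.

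Three further points are fair:

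- SAP section 11 places table specifications in a separate document, which might supply the missing footnote.
- The imputation is confined to tables, so with at most 42 subjects a reader could find unassessed events in the listings.
- The error overstates drug-relatedness, which is the cautious direction. It leaves the all-TEAE, severe and serious rows untouched, and no text ties dose escalation to these tables.

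None of this reconciles the protocol with itself. Section 10.1 still permits a blank that the endpoints and section 11.4 cannot accommodate, and the SAP still turns that permitted blank into a definite relationship. The listings do not correct the two summary displays, and a footnote that might exist elsewhere does not replace the one that the SAP omits.

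**Conclusion.** The concern holds. Protocol section 10.1 conflicts with the synopsis endpoints and section 11.4, and SAP section 7.1.1.3 resolves the gap by counting permitted blanks as drug-related, with no disclosure required. Confidence in the textual conflict is high.

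The size of the distortion cannot be established from the documents. It is nil if causality is always recorded, modest if about a tenth of ratings are blank (1.06- to 1.34-fold at subject level), and large if half are blank (1.25- to 2.33-fold). These ranges rest on assumed related shares of 20% to 50%, two independent TEAEs per subject, and blanks unrelated to true causality. The effect is limited to the related-TEAE row and the related-TEAE table by SOC and PT. It should be fixed because those two displays bear on the first primary objective and the correction is cheap.

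**What to change.** 1. **Protocol section 10.1:** delete the sentence that exempts non-serious AEs, and require an investigator causality rating for every AE on the eCRF. This brings collection into line with the endpoints and section 11.4.
2. **SAP section 7.1.1.3:** keep worst-case imputation for sporadic blanks only, and require a footnote for imputed causality as is already done for severity.
3. **If events have already been recorded without causality:** show not assessed as a separate category, and present the related-TEAE table with and without the imputation.
4. **One causality scale:** section 7.1.1.3 works with possible, probable and definite, while section 7.7.1 works with related, possibly related, unlikely or remote, and not related. The value that the SAP imputes is not one of the categories named in section 7.7.1, so the two need to be aligned.

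The cost is wording in both documents, a mandatory eCRF field if it is not already mandatory, a footnote, and at most one additional table. The extra site effort is small.
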